3.0 Records and reports of the monitor

Following each site initiation visit, periodic visit, and close-out visit, a follow-up letter to summarize the visit will be sent to the clinical site.

APPENDIX D Definitions

Adjunctive Therapy: Additional treatment necessary for achievement of clinical success immediately following treatment with the study device (Enforcer balloon) or control device (conventional balloon angioplasty). Adjunctive therapies may include high-pressure balloon angioplasty, cutting balloon angioplasty, stents or stent graft.

Adverse Event: Any untoward medical occurrence, unintended disease or injury, or untoward clinical signs (including abnormal laboratory findings) in patients, users, or other persons, whether or not related to the investigational medical device. Refer to Section 9.6: Adverse Events for a list of reportable events.

Anatomic Success: Residual stenosis less than 30% within the treated lesion following the study procedure (including adjunctive therapy).

Arteriovenous (AV) Hemodialysis Access Circuit (also Access Circuit, Dialysis Access Circuit):

- AV Fistula - The vascular conduit beginning from the arterial inflow (2 cm upstream from the AV anastomosis) and ending at the confluence of the cephalic and axillary veins.
- Graft – The vascular conduit beginning from the arterial inflow (2 cm upstream from the artery-graft anastomosis) and ending at the confluence of the cephalic and axillary veins.

AV Hemodialysis Access Circuit, Mature: Native fistula has been successfully used for at least one hemodialysis treatment. Grafts included in the study will have also been successfully used for at least one hemodialysis treatment.

Clinical or physiological abnormalities which indicate dialysis access dysfunction:

Abnormalities may include the following:

- Decreased access blood flow (e.g., <600ml/min, decrease in flow)
- Elevated venous pressure
- Decreased dialysis dose (Kt/V)
- Abnormal physical exam

Clinical Success: Resumption of normal dialysis for at least one session.

Conventional Angioplasty Balloon: A balloon catheter having a rated burst pressure less than 25 atmospheres.

Device Deficiency: Inadequacy of a medical device with respect to its identity, quality, durability, reliability, safety, or performance.

Device Success: Residual stenosis less than 30% within the treated lesion immediately after angioplasty with the study device (Enforcer or conventional angioplasty balloon).

Dissection: Linear filling defect due to disruption of the intima, staining within the vessel wall.

High-Pressure Angioplasty Balloon: A balloon catheter having a rated burst pressure greater than or equal to 25 atmospheres.

Numeric Rating Scale (NRS) for pain: Assessment of patient-reported pain using a scale from 0 to 10 where 0 indicates no pain and 10 indicates worst possible pain. Patients will be instructed to rate the pain they feel associated with the balloon inflations during the study procedure.

Occlusion: No flow can be identified through the study lesion.

Percent (%) stenosis: Estimated by comparing the closest segment of vessel having the most normal appearance (i.e. the reference vessel).

Primary Patency: Uninterrupted patency of the AV hemodialysis access circuit. Loss of primary patency occurs when a restenosis or occlusion of the AV hemodialysis access circuit results in:

- a reintervention or
- abandonment of the AV dialysis access

Reintervention: Any endovascular or surgical intervention performed in the study-treated AV hemodialysis access circuit.

Rupture: Disruption of the vessel wall allowing marked extravasation of contrast outside the vessel.

Serious Adverse Event: Adverse event that:

- a. Led to death,
- b. Led to serious deterioration in the health of the patient, that either resulted in:
 - i. A life-threatening illness or injury, or
 - ii. A permanent impairment of a body structure or a body function, or
 - iii. Medical or surgical intervention to prevent life-threatening illness or injury or permanent impairment to a body structure or a body function,

NOTE: Planned hospitalization for a pre-existing condition, or a procedure required by the study plan, without serious deterioration in health, is not considered a serious adverse event.

Thrombosis: Platelet or fibrin deposition within the treated segment successfully treated with thrombolysis or thrombectomy.

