9.6 Adverse Events

The following adverse events, occurring after the point of enrollment until the last day of patient participation, are to be reported to the sponsor using the appropriate eCRF:

- Events with potential relationship to the study device or study procedure
- Serious Adverse Events
- Restenosis or occlusion resulting in a reintervention or abandonment of AV dialysis access circuit

Information regarding occurrence of adverse events (including onset date, end date, date of awareness, event description, treatment, and whether the device or procedure contributed to the event) will be captured throughout the study and recorded on the appropriate eCRF.

Sites are responsible for following their normal reporting process (e.g., to manufacturer, to regulatory authority) for commercially available devices.

The sponsor is responsible for reporting events to the reviewing IRB(s) and principal investigator(s) as required according to applicable regulations/standards/policies.

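### The serious adverse event definition lacks the hospitalisation criterion that its own note implies, so a limited group of unrelated, non-access admissions has no reporting route

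*Combined protocol and SAP*

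**What the plan says.** Appendix D makes an adverse event serious by one of two routes. Item a is death. Item b begins "Led to serious deterioration in the health of the patient, that either resulted in" and then gives three results:

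- b.i: "A life-threatening illness or injury, or"
- b.ii: "A permanent impairment of a body structure or a body function, or"
- b.iii: "Medical or surgical intervention to prevent life-threatening illness or injury or permanent impairment to a body structure or a body function"

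The note directly below the list sets out what does not count as serious: "Planned hospitalization for a pre-existing condition, or a procedure required by the study plan, without serious deterioration in health, is not considered". Hospitalisation is mentioned nowhere else in the definition, and no other section makes it a criterion for seriousness or for reporting.

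Section 9.6 lists what sites report to the sponsor:

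1. "Events with potential relationship to the study device or study procedure"
2. "Serious Adverse Events"
3. "Restenosis or occlusion resulting in a reintervention or abandonment of AV dialysis access circuit"

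Section 9.4 and footnote a (attached to the ISO 14155 entry in Section 2.0) both restrict adverse event reporting to that list. Footnote a also allows reporting to wait until the 90-day chart review. Section 7.5.3 names adverse events as an additional measure. Section 11.3.3 applies the same analysis strategies to the additional measures and allows specific adverse events to be compared.

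**The concern.** The list and the note point in different directions. An exemption confined to planned admissions suggests that unplanned admissions can be serious, but on the list alone no admission is serious merely because it was an admission. One site could apply the list literally while another reads the note as implying a hospitalisation criterion, and each could say that it followed the plan. A monitor checking under Appendix C that events were appropriately reported has no text with which to settle the difference.

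This matters because seriousness is one of only three ways into the adverse-event data, and it is the only one that takes in events outside the access circuit regardless of relatedness. Where an admission meets no listed criterion and is not for access failure, its collection depends on the relatedness judgement. The bias-reduction measures in Section 7.4 are stratified randomisation, a cap on enrolment per site and uniform endpoint definitions. Blinding is not among them, no section describes independent adjudication of events, and the judgement may be made in retrospect at chart review.

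**Working it through.** No arithmetic applies: the point depends on no rate, margin or sample size. The check is to follow an unplanned admission within 90 days through Appendix D and then Section 9.6.

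| Unplanned admission | Appendix D criterion | Section 9.6 category | Reportable? |
|---|---|---|---|
| Potentially related to device or procedure | Not needed | 1 | Yes |
| Unrelated, fatal | a | 2 | Yes |
| Unrelated, serious deterioration with threat to life, lasting impairment, or preventive intervention | b.i, b.ii or b.iii | 2 | Yes |
| Unrelated, restenosis or occlusion with re-treatment or abandonment of the access | Not needed | 3 | Yes |
| None of the above | None | None | No on the list; arguable if the note is read as implying a criterion |

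Only the last row is lost, and it requires three conditions together:

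- none of a, b.i, b.ii or b.iii is met;
- the admission does not involve access failure of the kind in category 3;
- the investigator sees no potential relationship to device or procedure.

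Two further checks:

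- **Is the gap declared?** Footnote a says which events are reported. It does not say that the meaning of serious has been narrowed, and it does not mention hospitalisation. It therefore explains the closed list but not the mismatch inside the definition.
- **Which results could move?** The primary endpoint is adjunctive treatment immediately after the initial balloon (Section 7.5.1). The safety measures named in Section 7.5.2 are rupture, circumferential tears and reintervention/patency. None is defined by admission to hospital. What remains is the adverse-event measure of Section 7.5.3.

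One caution concerns the text itself. Items i to iii are numbered in sequence, so nothing appears to be missing in the middle, but item iii ends in a comma. A further item after it cannot be excluded without looking at the source page.

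**The case against.** The strongest reply is that the note can work without a hospitalisation criterion. It also exempts procedures that the plan requires, and its condition about deterioration repeats the stem of item b. It can thus be read as guarding against over-reporting under b.iii, where an intervention is the seriousness result. This stands to the extent that no event is called serious in one place and non-serious in another. A reader might infer that the definition contradicts itself; strictly, it does not. On the literal list the hospitalisation part of the note is redundant. It still invites two readings, and nothing else in the plan chooses between them.

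A reader might also infer that every unplanned admission not judged related goes unreported. The table shows otherwise: such admissions are reportable if they meet a or any part of b, or involve category 3 access failure. Nor must the investigator attribute the event to the device. A potential relationship is enough, and the procedure counts as well. That low threshold narrows the gap and makes reporting that differs by arm less likely. The documents contain no evidence that it would differ; the absence of stated blinding only leaves it possible.

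Finally, limited safety reporting is a disclosed choice for a commercially obtained, FDA-cleared device followed by chart review. That is a fair reason for a short reportable list. It does not account for a note that presupposes a criterion the list lacks, because footnote a is where departures are declared and this one is not there. It is also fair to say that the documents do not by themselves dictate a hospitalisation criterion. What they do require is that the list and the note be brought into line.

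**Conclusion.** The point holds in a limited form. The definition has no hospitalisation criterion although its note implies one, and the closed list in Section 9.6 turns that omission into a gap in collection for the admissions in the last row of the table. The consequence is incomplete and possibly inconsistent adverse-event data in a measure that may be compared between arms. The primary endpoint and the named safety measures do not change.

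The size of the gap cannot be stated, because the documents give no admission rates and no basis for splitting admissions by cause or relatedness. The conclusion assumes that the list in Appendix D is complete as printed. If a hospitalisation item does follow b.iii on the source page, the point falls away. This is an inexpensive improvement and not a threat to the trial's main result.

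**What to change.** First, check the source page of Appendix D for a list item after b.iii. If there is none, add unplanned or prolonged hospitalisation as a further result under item b and keep the note as its exception. Section 9.6 then needs no change, because its second category would take in these admissions whatever the relatedness judgement. The cost is one line in Appendix D and more events to enter at the 90-day chart review.

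If hospitalisation was left out on purpose, declare that in footnote a with the other departures from ISO 14155, and align the note with the list. That costs a sentence and removes the ambiguity, but these admissions would still not be collected. Deleting the note alone would tidy the wording without improving the data.
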